**Impact of the PCSK9 Inhibitor Evolocumab on the Pharmacodynamic Effects of
Clopidogrel in Patients with Atherosclerotic Cardiovascular Disease and
High or Normal On-Treatment Platelet Reactivity**

[name], PhD
University of Florida College of Medicine-Jacksonville
[name]
[name]
[contact]
[contact]
E-mail: [contact]

Background and Significance

Dual antiplatelet therapy (DAPT) with aspirin and a P2Y₁₂ receptor inhibitor represents the standard of care for the long-term secondary prevention of atherothrombotic events in patients with acute coronary syndrome (ACS) or undergoing percutaneous coronary intervention (PCI) [1]. Moreover antiplatelet therapy is commonly used in patients with other atherothrombotic disease manifestations, such as stroke and peripheral arterial disease (PAD). Clopidogrel is the most widely used P2Y₁₂ receptor inhibitor and is the only agent of this class currently recommended in patients with stable coronary artery disease (CAD) undergoing PCI, and for the treatment of stroke or PAD [2]. Although the efficacy of DAPT with aspirin and clopidogrel has been consistently shown in different clinical settings, rates of ischemic recurrences remain elevated despite this treatment regimen, especially in high risk patients [1,3]. This has been in part attributed to the high interindividual variability in responses to clopidogrel [3,4]. Clopidogrel is a pro-drug which requires a two-step metabolic transformation to exert its antiplatelet effect. Pharmacodynamic (PD) studies have shown that approximately 30-40% of patients experience high on-treatment platelet reactivity (HPR) while receiving clopidogrel treatment [3,4]. Importantly HPR status has been strongly associated with an increased risk of ischemic events, in particular stent thrombosis, in patients with ACS and following PCI [4]. This underscores the need for strategies aimed to reduce HPR rates in patients treated with clopidogrel. Several factors (clinical, cellular, and genetic) have been associated with HPR on clopidogrel [3,4]. Among these, genetic polymorphisms of the hepatic cytochrome P450 (CYP) 2C19 gene, the enzyme involved in both metabolic steps of transformation of clopidogrel pro-drug into its active metabolite, have shown to affect clopidogrel PD and pharmacokinetic and impact clinical outcomes [3,4]. In particular, the *2 and *3 loss-of-function

(LOF) allelic variants confer loss of enzyme function, which leads to attenuated clopidogrel bioactivation, lower platelet inhibition and worse outcomes [3,4].

Multiple approaches have been advocated to reduce HPR rates. Intuitively, the use of the more potent P2Y₁₂ receptor inhibitors prasugrel and ticagrelor represent potential treatment options [1]. However, their increased costs and risk of bleeding complications compared with clopidogrel have limited their broad uptake in clinical practice [1]. The pleiotropic effects associated with lipid lowering therapies, in particular statins, have been subject to extensive research [5]. In a previous study we showed that treatment with high-dose atorvastatin in addition to double-dose clopidogrel reduced platelet reactivity significantly more than double-dose clopidogrel alone in statin-naïve patients with stable CAD and HPR [6]. To date, the exact biological mechanisms involved in the statin modulation of platelet function are not fully understood, although likely attributed to both its lipid-lowering and non-lipid-related effects [7,8]. In fact, there is increasing evidence that circulating lipoproteins affect platelet function. In particular, LDL, VLDL, and especially oxidized LDL are atherogenic lipoproteins and increase platelet activation [9]. Also, familial hypercholesterolaemia is associated with increased platelet activity, such as hyperaggregability, and the application of a lipid-lowering drug resulted in a reduction of platelet reactivity [10].

Evolocumab is a monoclonal antibody targeting proprotein convertase subtilisin/kexin type 9 (PCSK9) that is administered subcutaneously (s.c.) at a dosage of 140 mg every 2 weeks or 420 mg once monthly [11]. In clinical trials in patients with primary hypercholesterolemia or mixed dyslipidemia, evolocumab was more effective than placebo and/or ezetimibe in reducing LDL cholesterol, including when added to statin therapy [11-13]. Importantly, in an exploratory analysis, the use of evolocumab plus standard therapy, as compared with standard therapy alone, significantly reduced the incidence of cardiovascular events [13]. Whether the reduction in cardiovascular events

is simply due to LDL reduction or might be related to other mechanisms is currently subject of investigation. Although LDL reduction with statin therapies has been associated with reduction in platelet reactivity, to date the effects on platelet aggregation of adjunctive lipid lowering with evolocumab has not been explored.

Study aims

The primary aim of the present study is to investigate the effects of evolocumab in addition to statin therapy on platelet reactivity in patients with atherosclerotic cardiovascular disease (ASCVD) while on clopidogrel treatment. Secondary aims will include the effects on cholesterol levels.

Research Plan

Study Population

Inclusion criteria:

1. Patients with ASCVD, defined as prior ACS, history of myocardial infarction, stable or unstable angina, coronary or other arterial revascularization, stroke, transient ischemic attack, or PAD presumed to be of atherosclerotic origin.
2. On therapy with clopidogrel (75mg od), with or without low-dose aspirin (81mg od), as per standard-of-care for at least 30 days.
3. HPR, defined as P2Y₁₂ reaction units (PRU) > 208 by VerifyNow P2Y₁₂, or normal platelet reactivity (NPR), defined as PRU between 85 and 208.

4. Fasting LDL-cholesterol ≥ 70 mg/dL or a non-high-density lipoprotein cholesterol (HDL-C) of ≥ 100 mg/dL after ≥ 2 weeks of optimized stable lipid-lowering therapy with maximally tolerated dose of statin, which would ideally include a high-intensity statin, but must be at least moderate intensity statin (i.e. atorvastatin 20 mg or equivalent, with or without ezetimibe. Maximal tolerated dose will be defined based on patient clinical history (no statin re-challenge will be performed).
5. Age ≥ 18 years old.

[figure not shown]
Exclusion criteria:

1. On treatment with any oral anticoagulant (vitamin K antagonists, dabigatran, rivaroxaban, apixaban, edoxaban).
2. On treatment with any antiplatelet agent other than aspirin and clopidogrel in the past 14 days.
3. Use of PCSK9 inhibitors in the past 90 days
4. Creatinine clearance < 30 mL/minute.
5. Known severe hepatic impairment.
6. History of a serious hypersensitivity reaction to evolocumab
7. Hemodynamic instability
8. Pregnant and breastfeeding women [women of childbearing age must use reliable birth control (i.e. oral contraceptives) while participating in the study].

Research Design

The proposed investigation will be a prospective, randomized, parallel-design, double-blind, placebo-controlled, PD study conducted in patients with ASCVD and HPR (PRU>208) or NPR (PRU 85-208) on clopidogrel. Patients with low platelet reactivity (PRU<85) will be excluded given that their distribution profile of platelet reactivity would be unlikely to unravel a platelet inhibitory treatment effect of evolucumab. The study will be performed at the University of Florida Health Science Center at UF Health Jacksonville - Division of Cardiology. Patients will be recruited in the Cardiology Clinics of our institution and will be screened by Cardiology Research staff, who will verify that all candidates meet inclusion and exclusion criteria. Results from blood tests performed within the last 90 days will be considered valid for screening purposes. If these are not available, a blood sample will be collected for the screening phase.

After providing written informed consent, patients meeting study entry criteria will be randomly assigned to receive either evolucumab 420 mg s.c. or placebo (0.9% sodium chloride s.c. injection). Blood sampling for PD testing will be conducted at 3 time-points: baseline, and 14±2 days and 30±2 days after randomized drug administration. At each time point, blood will be collected before the morning dose of clopidogrel, in order to measure trough levels of platelet inhibition. During study treatment major adverse cardiac events (death, MI, stroke, and urgent revascularization procedures) and serious adverse events (bleeding and other adverse events) will be collected. A flow diagram of the study design is illustrated below.

Laboratory testing

PD testing

Peripheral venous blood samples will be drawn through a short venous catheter inserted into a forearm vein and collected in citrate, EDTA, and serum tubes as appropriate for assessments. The first 2-4 mL of blood will be discarded to avoid spontaneous platelet activation. Blood sampling will be performed at 3 time points as indicated above in the study design section. Various PD assays will be performed as described below:

1. VerifyNow P2Y12
2. Light transmittance aggregometry (LTA)
3. Thrombelastograph Coagulation Analyzer TEG 6s Series system (CORAX[®] system)

Description of laboratory assays

1) VerifyNow (VN) P2Y12: The VerifyNow System is a turbidimetric based optical detection system which measures platelet induced aggregation as an increase in light transmittance (Accumetrics, San Diego, CA) and will be utilized according to manufacturer's instructions, as previously described [14]. The assay is based on microbead agglutination and uses specific reagents for the pathways of interest. The VN-P2Y12 assay, by combining ADP+PGE1, measures changes in

platelet function specific to P2Y₁₂ receptor inhibitors. The assay is based upon the ability of activated platelets to bind fibrinogen. Fibrinogen-coated microparticles aggregate in proportion to the number of GP IIb/IIIa receptors expressed. Microbead aggregation is more rapid and reproducible if platelets are activated; therefore the reagents are incorporated into the assay channel to induce platelet activation without fibrin formation. Light transmittance increases as activated platelets bind and aggregate fibrinogen-coated beads. The instrument measures this change in optical signal and reports results in P2Y₁₂ Reaction Units (PRU). HPR will be defined as PRU > 208 and NPR as PRU 85-208 [4].

2) Light transmittance aggregometry (LTA): Platelet aggregation will be performed using LTA according to standard protocols. Blood will be collected in citrated (3.2%) tubes. LTA will be assessed using platelet rich plasma (PRP) by the turbidimetric method in a 2-channel aggregometer (Chrono-Log 490 Model, Chrono-Log Corp., Havertown) as previously described [14]. Platelet agonists will include arachidonic acid (AA, 1 mM), collagen (3 µg/ml), ADP (5 and 20 µM), TRAP (15 µM). PRP will be obtained as a supernatant after centrifugation of citrated blood at 1000 rpm for 10 minutes. The isolated PRP will be kept at 37° C before use. Platelet poor plasma (PPP) will be obtained by a second centrifugation of the blood fraction at 2800 rpm for 10 minutes. Light transmission will be adjusted to 0% with the PRP and to 100% for the PPP for each measurement. Curves will be recorded for 6 minutes and platelet aggregation will be determined as the maximal percent change (MPA) in light transmittance from baseline using PPP as a reference. HPR will be defined as MPA with 20 µM ADP > 59% and MPA with 5 µM ADP > 46% [4].

3) TEG 6s Series system (CORA[®] system): the TEG 6s system (Haemonetics Corporation, Braintree, MA, USA) will be used according to manufacture instructions [15]. In brief, the CORA[®] system is a new generation portable thrombelastography technology able to evaluate all phases of

hemostasis, including time to clot formation, rate of clot formation, strength of clot and residual clot strength due to antiplatelet drugs, rate of clot lysis. Disposable assay cartridges contain all of the components necessary to allow the analyzer to prepare samples and perform hemostasis tests. The analyzer automatically draws the blood into the active area of the cartridge, meters the exact amount required for the test, and mixes it with the reagents spotted in the cartridge. The analyzer then monitors the harmonic motion of a pendant drop of blood in response to external vibration. As the sample transitions from a liquid state to a gel-like state during clotting, the modulus of elasticity and resonant frequency increase. The instrument measures these variations in resonant frequency during clotting and lysis. The results are displayed in a table and on a graphical tracing that reflects a hemostasis profile of clot formation. The resulting hemostasis profile is a measure of the time it takes for the first measurable clot to be formed, the kinetics of clot formation, the strength of the clot, and the breakdown of the clot, or fibrinolysis. In particular, the PlateletMapping Cartridge are used to assess platelet function in patients who have received platelet inhibiting drugs. The PlateletMapping assay consists of a set of agonists, ADP and AA platelet agonists together with ActivatorF, which can measure the inhibition of platelet function. This assay specifically determines the MA (Maximum Amplitude, a measure of clot strength) and the reduction in MA due to antiplatelet therapy and reports it as a percentage of reduction in clot strength. The assay uses AA and ADP agonists to generate test results that reflect the inhibiting effects of antiplatelet agents such as TxA₂ Inhibitors (e.g., aspirin) and ADP P₂Y₁₂ inhibitors (e.g., clopidogrel). Since thrombin (present in blood samples) is the primary and most potent activator of platelets, its activity must be inhibited with heparin so that the platelet activating effects of ADP and AA can be measured. Since thrombin has been rendered inactive by heparin, activatorF is used to replace thrombin's role in the conversion of fibrinogen to fibrin and Factor XIII to Factor XIIIa. Thus, with this cross-linked fibrin

network as the foundation, additional clot strength due to platelet-fibrin bonding related to ADP and AA platelet receptor activation can be measured. The HKH reagent, a combination of kaolin and heparinase, generates test data for the uninhibited MA resulting from thrombin activation of the blood sample, while the heparinase neutralizes the effects of heparin. The HKH test provides measures of R (Reaction time; the amount of time between the start of the test and the beginning of coagulation), K (the speed of formation of the clot from R time to a specific clot strength), Angle (the speed of clot strengthening), LY30 (Percent lysis 30 minutes after MA is finalized) and MA parameters; The activatorF test provides the contribution of fibrin to the overall strength of the clot. This test value is used in the calculation of aggregation/inhibition for MA ADP and MA AA. The AA and ADP test provide measures of MA, percent inhibition and percent aggregation. HPR will be defined as MA ADP > 47 mm [15].

Genetic testing

Spartan RX rapid genotyping: Spartan RX (Spartan Bioscience Inc., Ontario, Canada) is the rapid genotyping system determining the CYP2C19 (*1,*2,*3,*17) allele status within 1 hour [16]. This test consists of four separate steps intended to be done in less than 8 minutes: acquisition of a buccal swab; insertion of the swab into the cartridge; insertion of the reaction solution into the device; and analysis of CYP2C19 genotype triggered by a button on the device.

Lipid profile and PCSK9 levels

Blood for the evaluation of the effects on lipids will be drawn at the same time points as described above for PD measurements. Cholesterol measures will include a standard lipid profile and lipoprotein(a) [Lp(a)], which will be measured by the central laboratory of our institution

according to standard protocols. At each time point, blood samples samples will also be stored for measurement of PCSK9 serum levels and for possible future analyses. PCSK9 levels will be measured by ELISA as previously described [17].

Study endpoints and sample size calculation

The primary end point of our study is the reduction in platelet reactivity, as defined by PRU, between evolocumab and placebo at 30 days after randomization in each cohort. We hypothesize that evolocumab therapy will be associated with a reduction of 30 PRU in patients with HPR and NPR. The rationale for considering a reduction of 30 PRU is because this value approximates that observed with more intense lipid lower therapy using statin therapy [18]. Statistical assumptions were derived for each cohort of patients based on distribution of their PRU levels from a cohort of subjects on maintenance clopidogrel therapy (HPR: 247 ± 29 ; NPR: 150 ± 35). In patients with HPR, 17 patients per group (34 total) are needed to detect a 30 PRU difference with 80% power. In NPR patients, 23 patients per group (46 total) are needed to detect a 30 PRU difference with 80% power. Therefore, under the assumption of a 30 PRU reduction with evolocumab compared with placebo in each cohort, 80% power and α of 0.05, 80 total patients with a valid primary end point will be needed. Considering a possible dropout rate of 10%, up to 90 patients will need to be randomized. We anticipate that up to 500 patients will need to be screened to reach our sample size. Given the absence of preliminary studies exploring the effects of PCSK9 inhibitors on platelet aggregation the expected reduction in PRU was arbitrarily defined.

Other endpoints will include the comparisons between evolocumab and placebo of all PD parameters measured by multiple assays, and of cholesterol levels at each time point. Exploratory analyses will assess the differential response to evolocumab treatment according to the presence of

LOF genetic polymorphisms as well as the levels of PCSK9. We will also investigate different response profiles in patients with and without aspirin.

Statistical analysis plan

Categorical variables will be expressed as frequencies and percentages. Continuous variables will be presented as mean \pm SD or median [IQR]. An analysis of covariance (ANCOVA) method with a general linear model will be used to evaluate the primary end point as well as all between-groups comparisons of platelet reactivity, cholesterol levels and HS-CRP. The Fisher's exact test or Pearson's chi square test will be used to evaluate t comparisons of HPR and NPR rates between groups.

A 2-tailed p value of < 0.05 will be considered to indicate a statistically significant difference for all the above analyses. Statistical analysis will be performed by our group using SPSS v22.0 software (SPSS Inc. Chicago, IL).

Publication Strategy/Additional Information

Study subjects will be identified first (months 1-24): we expect to enroll 3-4 subjects monthly and complete enrollment in 24 months (total: 90 subjects randomized). Month 25 will be implied for statistical analysis and months 26-27 for manuscript preparation. We intend to present data at a major scientific meeting at completion of the study.

Possible Discomforts and Risk

In clinical trials, the most commonly reported adverse events with evolocumab included nasopharyngitis (4.0% of evolocumab recipients vs. 3.9% of controls), arthralgia (1.8% vs. 1.6%), myalgia (2.0% vs. 1.8%), upper respiratory tract infection (2.1% vs. 2.2%), back pain (2.3% vs. 2.2%), and nausea (1.8% vs. 1.2%). Injection-site reactions were reported in 3.3% of evolocumab recipients and 3.0% of controls. Allergic reactions occurred in 5.1% and 4.7% of evolocumab-treated and placebo-treated patients, respectively. The most common allergic reactions were rash (1.0% vs. 0.5% for evolocumab and placebo, respectively), eczema (0.4% vs. 0.2%), erythema (0.4% vs. 0.2%), and urticaria (0.4% vs. 0.1%) [19].

All clinical events described above, if they were to occur, as well as death, myocardial infarction, stroke, and urgent revascularization procedure with PCI or coronary artery bypass grafting will be recorded. Clinical events will be evaluated by a local committee, comprised of 2 faculty members (2 cardiologists), not directly involved in the research. In the event of a report of a serious adverse event, the local committee will meet and treatment management will be managed according to physician recommendation.

Definition of Adverse Events

An adverse event is any unintended or undesirable experience that occurs during the course of the clinical investigation whether or not it is considered to be therapy related. This includes any newly occurring event or previous condition that has increased in severity or frequency since the initiation of study treatment. Adverse events will be followed until resolution while the patient remains on-study. Once the patient is removed from study, events thought to be related to the study therapy will be followed until resolution or until the patient starts a new treatment regimen.

Serious Adverse Events (SAE): An adverse event occurring while on study that results in any of the following outcomes:

- Death
- A life-threatening adverse experience.
- A persistent or significant disability, incapacity, or is a congenital anomaly, or birth defect.
- Requires inpatient hospitalization, or prolongation of existing hospitalization.

All SAEs will be collected, recorded and reported, whether or not considered causally related to the study drug, or to the study procedure(s). Study related SAE is defined as SAE occurring while on study and considered related (reasonable possibility that the study treatment caused the adverse experience) to the study treatment.

The definition of serious adverse event also includes ‘important medical event’. Medical and scientific judgment should be exercised in deciding whether expedited reporting is appropriate in other situations, such as important medical events that may not be immediately life-threatening or result in death or hospitalization but may jeopardize the patient and/or may require medical or surgical intervention to prevent one of the other outcomes listed in the definition above. These should also usually be considered serious. Examples of such events are intensive treatment in an emergency room or at home for allergic bronchospasm; blood dyscrasias or convulsions that do not result in hospitalization; or development of drug dependency or drug abuse.

All suspected unexpected serious adverse reactions (SUSARs) related or possibly related to evolocumab and their follow-up reports will be reported to Amgen within 24 hours of submission to the regulatory agency, IRB or IEC. A copy of any safety report involving an Amgen drug (e.g. evolocumab) submitted to the regulatory agency, IRB or IEC, will be faxed to Amgen, within 24

hours of such submission. All pregnancies and pregnancies occurring in the partner of a patient participating in the study will be reported within 10 calendar days of Investigator's awareness.

Possible benefits

The present investigation is aimed to evaluate the PD effects of evolocumab as an add-on therapy to standard antiplatelet treatment in patients with CAD. This study is not designed to evaluate differences in clinical benefit. However, differences in antiplatelet profiles may potentially prompt further investigations of the clinical implication of this difference by means of a larger scale clinical study.

Potential Financial Risks or Benefits

None

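### Does stating enrolment only as a total leave the separately powered HPR and NPR cohorts unprotected?

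*Combined protocol and SAP*

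**What the plan says.** *Study endpoints and sample size calculation* places the primary comparison at 30 days within each cohort and sizes the cohorts one at a time. For HPR: "In patients with HPR, 17 patients per group (34 total) are needed to detect a 30 PRU difference with 80% power". For NPR: "In NPR patients, 23 patients per group (46 total) are needed to detect a 30 PRU difference with 80% power". The next sentence draws the total as a consequence of these two: "80 total patients with a valid primary end point will be needed". After an allowance of 10% for dropout, "up to 90 patients will need to be randomized". On screening, the section adds: "We anticipate that up to 500 patients will need to be screened to reach our sample size".

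*Publication Strategy/Additional Information* repeats the total and does not split it: "complete enrollment in 24 months (total: 90 subjects randomized".

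*Research Design* says that "patients meeting study entry criteria will be randomly assigned to receive either evolucumab 420 mg s.c. or placebo", with no mention of strata or blocks, and then announces a figure: "A flow diagram of the study design is illustrated below". That figure is not reproduced in the text available for this review.

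**The concern.** Two tests, each with its own power claim, share one enrolment total. The evaluable total of 80 is exactly 34 + 46, so any other mix puts one cohort below its stated size. The readable text does not give the number to randomise in each cohort, does not say that a cohort closes when full, and does not mention randomisation within cohorts.

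The plan's mix requires 34/80 = 42.5% HPR among evaluable patients. The only frequency in the document is 30–40% HPR among clopidogrel patients in general (*Background and Significance*), before patients with PRU below 85 are excluded. If patients were taken as they came until the total was reached, chance and the clinic population would set the mix. A null result in the short cohort could then reflect too few patients rather than no effect.

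**Working it through.** **Inputs** (*Study endpoints and sample size calculation*; two-sided testing from *Statistical analysis plan*): difference 30 PRU, SD 29 (HPR) and 35 (NPR), alpha 0.05 two-sided, 17 and 23 per group, 10% dropout.

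**1. The plan's own figures.** For a two-sample t-test with n1 and n2 per arm, the noncentrality is 30 / (SD × √(1/n1 + 1/n2)) on n1 + n2 − 2 degrees of freedom.

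- HPR, 17/17: 30 / (29 × √(2/17)) = 30 / 9.95 = 3.02 on 32 df; power 83.3%.
- NPR, 23/23: 30 / (35 × √(2/23)) = 30 / 10.32 = 2.91 on 44 df; power 81.1%.

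The smallest sizes reaching 80% by this method are 16 per group (80.8%) and 23 per group, so the stated 17 and 23 are adequate.

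**2. The randomised total.** By cohort: 34/0.9 = 37.8, rounded up to 38; 46/0.9 = 51.1, rounded up to 52; sum 90. On the total: 80/0.9 = 88.9, rounded up to 89. The stated 90 matches the cohort-level calculation exactly, although it could also be 89 rounded to a convenient number.

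**3. How exact the mix must be.** Power with 80 evaluable patients and arms as even as possible:

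| HPR / NPR | HPR power | NPR power |
|---|---|---|
| 28 / 52 | 75.0% | 85.8% |
| 31 / 49 | 79.4% | 83.6% |
| 32 / 48 | 80.8% | 82.8% |
| 34 / 46 (plan) | 83.3% | 81.1% |
| 35 / 45 | 84.3% | 80.2% |
| 36 / 44 | 85.4% | 79.3% |
| 40 / 40 | 89.0% | 75.2% |

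Both tests hold 80% from 32/48 to 35/45, and a miss of a few patients beyond that costs a few points.

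**4. The worst reading: no cohort numbers observed.** Assumptions: HPR count is Binomial(80, p), and p is not in the document. If 10–20% of clopidogrel patients are excluded for PRU below 85 (assumed), p lies between 0.30/0.90 = 33% and 0.40/0.80 = 50%. Average power uses simple 1:1 allocation; the chances use even arms.

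| HPR share | Average power HPR / NPR | Chance either test is below 80% | below 75% | below 70% |
|---|---|---|---|---|
| 33% | 70% / 86% | 90% | 61% | 42% |
| 40% | 79% / 82% | 67% | 18% | 7% |
| 42.5% | 81% / 80% | 65% | 14% | 4% |
| 44% | 83% / 79% | 67% | 16% | 3% |
| 50% | 88% / 74% | 87% | 46% | 16% |

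The high figures in the 80% column count 31 HPR (79.4%) or 44 NPR (79.3%) as failures. For shares of 40–44%, a loss to below 75% is uncommon.

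**5. Uneven arms if randomisation is not stratified.** Averaged over a Binomial(n, 0.5) split at the planned cohort sizes, power moves from 83.3% to 82.1% (HPR) and from 81.1% to 80.2% (NPR). A 13:21 split in HPR still gives 81.1%.

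**6. Feasibility.** If the 30–40% applies to those screened, 500 patients contain 500 × 0.30 = 150 to 500 × 0.40 = 200 with HPR, before the other entry criteria and consent, against 38 to be randomised. Filling the HPR cohort looks achievable.

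**The case for a change.** The strongest case for a change is that the text calls 34 and 46 the evaluable numbers needed and never calls them enrolment targets. Enrolment is stated twice, both times as a total, and nothing written stops one cohort from overrunning at the other's expense. At a 33% HPR share the HPR test would average 70% power; at 50% the NPR test would average 74%. Writing down 38 and 52 would add no patients. The text also does not say whether the screening PRU, for which results up to 90 days old are accepted, or the baseline PRU assigns the cohort, so a patient near 208 could fall on either side.

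What stands is that these details are unwritten. What does not stand is that the plan permits an arbitrary mix. The total is presented as following from the two cohort requirements, and nowhere is enrolment described as first come, first served. A team that stopped at 80 evaluable with 26 HPR would have failed a number that its own plan says is needed. The larger losses require both that departure and an HPR share that the document does not give. They also come from an unadjusted t-test, whereas the plan specifies ANCOVA. If baseline PRU were the covariate, with an assumed correlation of 0.3 or 0.5, 28 HPR patients would give 79% or 86% power rather than 75%. No correlation is stated, so this gain is only illustrative.

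The absence of stratification cannot be established while the design diagram is unavailable, and it would matter little for power.

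**Conclusion.** No change to the plan follows. This is missing operational detail that investigators who sized each cohort separately can be expected to fill: recruit to each cohort's number and close it when full. The stated cohort sizes reproduce (83.3% and 81.1% power), their inflation for dropout sums to the stated 90, and modest departures from the planned mix, 32/48 to 35/45, keep both tests at or above 80%.

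This rests on reading 34 and 46 as requirements, which the derivation of the total supports, and on the plan's SDs and 30 PRU difference. It would fail only if enrolment ran to the total without regard to cohort and the HPR share among eligible patients lay well away from 42.5%. The cohort-level randomisation numbers (38 and 52) and the PRU value that assigns the cohort could be recorded in the trial's working documents.

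### The day-30 ANCOVA leaves out of the primary comparison patients who have a day-14 PRU but no day-30 PRU; a longitudinal model would use them, for a modest and conditional gain

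*Combined protocol and SAP*

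**What the plan says.** Under Study endpoints and sample size calculation, the primary end point is the "reduction in platelet reactivity, as defined by PRU, between evolocumab and placebo at 30 days after randomization in each cohort". The cohorts are sized at 17 per group (HPR) and 23 per group (NPR), from which the section concludes that "80 total patients with a valid primary end point will be needed". It then adds: "Considering a possible dropout rate of 10%, up to 90 patients will need to be randomized".

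Under Research Design, PD blood is drawn at baseline and at "14±2 days and 30±2 days after randomized drug administration", so every patient who attends has a PRU about halfway to the primary time point.

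Under Statistical analysis plan, the primary end point and the other between-group comparisons of platelet reactivity are evaluated by ANCOVA in a general linear model. No covariate, analysis set, missing-data method or sensitivity analysis is named. PD parameters are also compared between arms as other end points, and the wording can be read to cover each visit.

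**The concern.** An ANCOVA of day-30 PRU needs a day-30 PRU. Because the plan defines no analysis set, the default is that patients without a valid day-30 value drop out of the primary comparison, including those who gave a day-14 sample.

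That analysis is unbiased if, given arm and the covariates in the model, the chance of a missing day-30 value is unrelated to post-dose PRU. A model of both visits needs less: missingness may also depend on the observed day-14 PRU. With only 17 and 23 evaluable patients per arm, a few losses related to response can move a cohort's estimate. The day-14 measurements that would help are already being collected.

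**Working it through.** **1. The plan's own figures.** Inputs: difference 30 PRU; SDs from "HPR: 247 ± 29 ; NPR: 150 ± 35"; "80% power and α of 0.05", two-sided.

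- Per group, n = 2(1.96 + 0.84)² × SD² / 30². HPR: 2 × 7.85 × 841 / 900 = 14.7, so 15. NPR: 2 × 7.85 × 1225 / 900 = 21.4, so 22. The t-test version gives 16 and 23, against 17 and 23 stated. Power at the stated n is 83.3% and 81.1%.
- Dropout: 34/0.9 gives 38 and 46/0.9 gives 52, together 90. Then 90 − 80 = 10 patients (11.1%) without a primary value.

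The sample size reproduces and is not at issue.

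**2. What the longitudinal model does.** When the only gaps are missing later visits, its day-30 effect is b30 = c + k × b14. Here b14 is the baseline-adjusted arm effect at day 14 in everyone with a day-14 value. The terms c and k are the arm and day-14 coefficients for day-30 PRU in completers, also adjusted for baseline. If no dropout has a day-14 value, b14 comes from the same completers and b30 is exactly the completer ANCOVA estimate. The gain therefore depends on dropouts having a day-14 sample.

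**3. Precision under random dropout.** With a fraction f missing and partial correlation r between days 14 and 30 given baseline, the ratio of standard errors (model/completer) is √(1 − f r²). For a common between-visit correlation ρ, r = ρ/(1 + ρ).

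- ρ = 0.3, f = 0.10: r² = 0.053, ratio 0.997.
- ρ = 0.85, f = 0.10: r² = 0.211, ratio 0.989.

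Simulation at 38 and 52 patients gave 0.989 to 1.000. Other assumed structures gave reductions of 0-3% and 1-4%. At f = 0.10 the ceiling is 1 − √0.9 = 5%.

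**4. Bias under PRU-related dropout.** The true effect is 30 PRU throughout. Correlations, dropout rules and day-14 availability are all assumed.

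HPR-type cohort, 19 per arm, 4000 trials per setting, simulation error about 0.2 PRU. The underlying level has mean 240 and SD 25, with visit error SD 20-25, shared post-baseline drift SD 0-30 and no entry cut-off:

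| Dropout rule | Completer ANCOVA | Longitudinal |
|---|---|---|
| 40% loss if day-14 PRU > 260 (7-9% lost) | 28.1-29.1 | 29.9-30.3 |
| Same, half of dropouts lack day 14 | 28.0-29.3 | 29.1-29.7 |
| Loss driven by unseen day-30 PRU | about 27.2 | 27.5-28.8 |
| Random loss | unbiased | unbiased |

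Under a milder rule (14% loss if day-14 PRU > 208), both estimates are within 1 PRU of the truth.

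With the plan's HPR 247 ± 29 and entry above 208, the first rule gave 28.8-29.2 (completer) and 30.1 (longitudinal). Across PRU-related dropout settings using both cohorts' stated means, SDs and entry limits, completer estimates were 27.2-29.4 and longitudinal 28.1-30.1. The completer bias is thus 30 − 29.4 = 0.6 to 30 − 27.2 = 2.8, about 1-3 PRU.

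**5. Share of bias removed.** Large-sample simulation: SD 35, 10% dropout per arm, PRU-related in the evolocumab arm only (logistic slope 1.5 per SD), ρ from 0.3 to 0.85:

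| Dropout depends on | All dropouts have day 14 | Half do | None do |
|---|---|---|---|
| Observed day-14 PRU (completer bias 0.5-1.1 PRU) | about 95-100% | 51-58% | 0% |
| Unseen day-30 PRU (completer bias 1.3-4.0 PRU) | 5-19% | 3-11% | 0% |

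Here the completer analysis overstates the effect, because high-PRU patients leave the treated arm only. In step 4 it understates it. The direction depends on the assumed mechanism.

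**6. Scale.** The unadjusted standard error is 29 × √(2/17) = 9.9 PRU in HPR and 35 × √(2/23) = 10.3 in NPR. A bias of 1-3 PRU is roughly 0.1-0.3 of that.

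**The case against.** The strongest reply is that nothing in the plan is wrong. The sentence about 80 patients concerns sample size; it does not define who is analysed. Completer ANCOVA is valid under random dropout. The trial is double-blind, has no PRU-based withdrawal rule and ends at about day 30, so strongly PRU-related loss is not obviously likely. The 260 cut-off is invented, and in NPR it lies (260 − 150)/35 = 3.1 SD above the mean, so that rule would lose almost nobody there. With entry limits applied, the same rule costs HPR about 1 PRU.

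Most of this stands, and it limits the size of the point. It does not answer that the primary method, as written, has no way to use a post-dose PRU already in hand, and that using it rests on a weaker assumption at almost no cost.

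Three stronger readings are tempting, and the documents do not support them:

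- **That day-14 PRU is discarded.** It is unused only in the primary comparison, for patients with no day-30 value; the other end points may use it.
- **That the model removes most of the dropout bias.** That needs dropout driven by observed PRU and a day-14 sample from most dropouts. The plan states neither, and the 10% may include patients lost before day 14.
- **That high-PRU patients will leave and so shrink the effect.** No passage says who leaves, and step 5 gives the opposite direction.

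**Conclusion.** The point holds as a modest improvement to the primary analysis, not as the correction of an error. About 10 of 90 randomised patients are expected to have no valid day-30 PRU, and the planned ANCOVA would in practice leave them out even where a day-14 value exists.

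Under assumed PRU-related dropout of about 4-11%, completer bias is about 1-3 PRU of 30; the deliberately one-sided setting in step 5 spans 0.5-4.0. How much the longitudinal model recovers runs from nearly all to none, depending on why patients leave and whether they reach day 14. In no setting run was it materially worse than the completer analysis. These sizes rest on assumed correlations and dropout mechanisms, since the documents give none.

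**What to change.** Before unblinding, amend the Statistical analysis plan section as follows.

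- **Primary analysis, in each cohort:** a linear mixed model with day-14 and day-30 PRU as responses; terms for treatment, visit, treatment-by-visit and baseline PRU-by-visit; unstructured covariance; all randomised patients with any post-dose PRU, analysed as randomised. The day-30 treatment contrast is the primary result. With complete data it equals a day-30 ANCOVA adjusted for baseline PRU only. The SAP names no covariate, so state that baseline PRU is the one intended.
- **Sensitivity analyses:** completer ANCOVA at day 30, and one analysis for departures from missing at random, such as shifting the missing day-30 values by a range of amounts in each arm. Completer ANCOVA alone does not test that assumption.
- **Reporting:** by arm and cohort, the number with no post-dose PRU, with day 14 only and with day 30, and the reasons. This shows how much the model could recover.

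The cost is a few lines of text. No new data, visits or patients are needed, the sample size is unchanged, and the named software can fit the model.
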